#### C4. Data Analysis

The PI(s) will be responsible for and supervise data collection and data management. Data will be stored in a locked cabinet in the PI's office. Data analysis will be conducted using standard statistical software including SPSS and R. Data will be analyzed through linear models including (M)ANOVA, repeated measures analyses and mixed linear model procedures to deal with correlational effects. This will be followed by appropriate post-hoc analyses comparing specific conditions. In order to maintain anonymity in data files participants will be only listed with their unique identification code. Data backup of these files and hard copies of data capture forms will be kept in locked files to which only authorized study personnel will have access. Descriptive data will be provided for all participants (e.g., mean age, sex, education, etc.). Clinical rating scales will be scored as they are in clinical use. There is no power analysis as this is an exploratory study.

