#### **Hypothesis: Acute Effect**

##### **Hypothesis 1.1**

Distress associated with pain as measured by the West Haven-Yale Multidimensional Pain Inventory (WHYMPI) (affective subscale) and pain anxiety symptom scale (PASS-20) will decrease after ten (10) days of active but not sham stimulation.

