## **C. Experimental Method**

### **C1. Brief Description of Subjects**

Participants will be aged over 18 years old with a diagnosis of chronic low back pain based on the inclusion criteria (see below) by a referring physician. Participants will be of any racial or ethnic group and of either sex. A questionnaire will be administered to screen for possible contraindications for tDCS (see exclusion criteria). We will consent up to thirty (30) volunteers with a goal of enrolling twenty (20) participants, ten (10) in the treatment group and ten (10) in the control group.

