### **C2. Study Design**

The study includes a screening visit, ten (10) study treatment session visits on consecutive weekdays and a follow-up phone call, approximately six (6) weeks after the last study visit. The ten study visits will occur at Butler Hospital and will take between two (2) to two and half hours (2 ½) hours. The total duration of this study for the participant is expected to be up to approximately twenty- four (24) hours; this includes the consent process, screening and eligibility assessments and ten research visits which will include the study treatment, tDCS, completion of study related questionnaires, and the follow-up phone call.

Half of the participants will receive only sham stimulation for all treatment days (days where tDCS is applied) and half will receive only active stimulation; this will be randomly assigned. Comprehensive measures of distress resulting from CLBP will be administered to assess both the short and longer term effects of tDCS treatment. Participants and research staff administering outcome scales will be blinded to active vs. sham tDCS.

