Pain Acceptance CPAQ-8	O		X		X	X
Emotional Distress PHQ-9 (Depression) GAD-7 (Anxiety) PASS-20 (Pain related fear/avoidance)	O O O		X X X		X X X	X X X
Psychiatric History MINI	I	X				
Sleep Measure Sleep assessment	O		X	X	X	X
Patient Expectation and Satisfaction CEQ CSQ-8	T T		X X		X* X* *(only session 10)	

Assessment instruments are used for the following purposes: I= Inclusion criteria; T = Treatment Development Target Assessment; O = Outcome Measure

Links to the measures, when available:

[DVPRS](#)

Date most recently revised (m/d/y): 03/03/2015

Protocol Version (if applicable): 5.0

[WHY-MPI](#)

[RMDQ](#)

[CPAQ-8](#)

[PHQ-9](#)

[GAD-7](#)

[PASS-20](#)

[CEQ](#)

[CSQ-8](#)

**Study Visits:** All participants will be clearly directed to the building and room where the study procedures will occur prior to each visit. All study visits will occur at Butler Hospital in a research room.

On the first day of treatment, prior to the tDCS treatment, females of childbearing age will be required to have a urine pregnancy test (hCG dipstick) before any study procedures. The test will be administered by a trained member of the research staff overseen by [name] or another licensed physician. Any participants that show a positive pregnancy test will be considered a screen failure.

Participants will be asked to complete the DVPRS, WHY-MPI, RMDQ, CPAQ-8, PHQ-9, GAD-7, PASS, CEQ, CSQ-8, and the Sleep Measure. This will provide a baseline measure in regards to the sensory/perceptual component of their pain, the degree to which pain interferes with daily activity, and the emotional component of their pain.

Prior to this and each study treatment, designated research staff will assess the skin on the participant's scalp where the electrodes will be placed to assure there are no lesions, cuts, or exclusionary skin disorders. Participants will be positioned for optimal comfort on a chair, recliner or stretcher. Designated trained research staff will attach the electrodes to the participant's scalp (participants will not need to have any hair shaved) and apply the flexible rubber headband to keep them in place. (See detail below). Participants will be educated that research staff will be monitoring them continuously through a non-recording closed-circuit camera from another room or he/she will be physically present in the room to assess if they need anything or want to stop the tDCS.

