The participant will then receive either the sham or active tDCS stimulation based on their random group assignment for twenty minutes (tDCS details are below). Following tDCS stimulation, only the DVPRS will be repeated. This measure will be used to determine whether immediate pain relief following stimulation occurs. Lastly, in order to monitor the effectiveness of the blind, participants will be asked to guess which treatment, active or sham, they received.

On subsequent treatment days, the DVPRS will be repeated before and after stimulation and the Sleep Measure will be repeated before stimulation. At the end of the first week of treatment, session five, in addition to the DVPRS and the Sleep Measure, the WHY-MPI, RMDQ, CPAQ-8, PHQ-9, GAD-7, and the PASS, will be repeated. During the second week, the DVPRS will again be administered before and after each treatment, and the Sleep measure will be repeated before stimulation.

On the final day of treatment, in addition to the DVPRS and the Sleep Measure, the WHY-MPI, RMDQ, CPAQ-8, PHQ-9, GAD-7, CEQ, CSQ-8, and the PASS, will be repeated.

Date most recently revised (m/d/y): 03/03/2015

Protocol Version (if applicable): 5.0

Follow-up assessments will occur by phone approximately six (6) weeks after the last tDCS treatment session and will consist of these same measures as session ten.

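### C4 does not say how the session-1 score enters the analysis; with 10 per arm, stating a baseline-adjusted comparison would usually gain precision from data already collected

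*Combined protocol and SAP*

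**What the plan says.** C4 (Data Analysis) is the whole analysis plan. It says "Data will be analyzed through linear models including (M)ANOVA, repeated measures analyses and mixed linear model procedures to deal with correlational effects", to be followed by post-hoc comparisons of specific conditions. It gives no model terms, covariates, baseline handling or primary contrast. It also says "There is no power analysis as this is an exploratory study".

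The design supplies a baseline score. Under C3, the questionnaires are completed on the first treatment day before stimulation: "This will provide a baseline measure in regards to the sensory/perceptual component of their pain". The outcome scales are repeated at session 5 ("At the end of the first week of treatment, session five, in addition to the DVPRS and the Sleep Measure", with the other scales listed after it), at session 10, and by phone about six weeks later, when the assessments "will consist of these same measures as session ten".

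Allocation is parallel and random (C2: "half will receive only active stimulation; this will be randomly assigned"), with a "goal of enrolling twenty (20) participants, ten (10) in the treatment group and ten (10) in the control group" (C1). The hypotheses refer to particular visits: under Hypothesis 1.1 distress "will decrease after ten (10) days of active but not sham stimulation", and the Aim 2 hypotheses concern the follow-up call.

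**The concern.** Several different analyses fit C4's wording: the session-10 score alone, a change from session 1, a group-by-time test over four visits, a group effect averaged over all visits, and a comparison adjusted for the session-1 score. They use the baseline differently and do not have the same precision.

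In the common forms of the named models, session 1 is one more repeated level. The group main effect then averages in a visit at which no treatment effect can exist. The group-by-time test spreads 3 df over four visits (4 − 1 = 3), whereas each aim concerns one visit.

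At stake are the width of the interval for the active-sham difference in a trial of 20 people, and whether the use of baseline is settled before or after the data are seen.

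**Working it through.** **Plan's own figure.** There is none to reproduce. C4 gives no power, effect size, SD, alpha or correlation.

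**Inputs from the documents.** n = 10 per arm; random 1:1 allocation; scales at sessions 1, 5, 10 and six weeks.

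**Assumptions.** True difference d = 1 SD at session 10; SD = 1 at each visit; two-sided alpha 0.05; no dropout; session-1-to-session-10 correlation r varied from 0 to 0.8.

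**Formulas.** Power comes from the noncentral t with noncentrality d / (s × √(2/10)). Here √(2/10) = 0.447, and s depends on the analysis:

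- Session-10 score alone: s = 1, 18 df.
- Change from session 1, which is the 1-df group-by-time contrast between sessions 1 and 10: s = √(2(1 − r)), 18 df.
- Session-1 score as covariate: s = √((1 − r²) × (1 + 1/16)), 17 df. The factor 1 + 1/16 = 1.0625 allows for estimating the slope in 20 people.

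Example at r = 0.5:

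- Score alone and change both have s = 1, so noncentrality is 1/0.447 = 2.24 and power 56%.
- Adjusted has s = √(0.75 × 1.0625) = 0.893, so noncentrality is 2.236/0.893 = 2.50 and power 66%.

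| r | Session-10 score alone | Change contrast | Baseline-adjusted | Gain over score alone (points) | Gain over change (points) |
|---|---|---|---|---|---|
| 0 | 56% | 32% | 53% | −3 | +21 |
| 0.3 | 56% | 43% | 57% | +1 | +14 |
| 0.5 | 56% | 56% | 66% | +9 | +9 |
| 0.6 | 56% | 66% | 72% | +16 | +7 |
| 0.7 | 56% | 78% | 82% | +25 | +4 |
| 0.8 | 56% | 92% | 93% | +36 | +1 |

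Gains are taken from unrounded powers. Simulation with 6,000 trials per setting at r = 0.3 / 0.5 / 0.7 gave 58 / 66 / 82% adjusted, 43 / 57 / 78% change, and 56 / 57 / 56% score alone.

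**Where the gain stops.**

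- Against the score alone, variances break even when (1 − r²) × 1.0625 = 1, that is r = √(1 − 1/1.0625) = 0.24.
- Against change, they break even when (1 + r) × 1.0625 = 2, that is r = 0.88.

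**Detectable difference at 80% power (SD units).**

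- r = 0.5: 1.32 score alone, 1.32 change, 1.19 adjusted.
- r = 0.7: 1.32, 1.03 and 0.98.

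**Readings that C4 permits but does not commit to.** These assume four equally correlated visits, r = 0.5 to 0.7, and effects at sessions 1, 5, 10 and six weeks of 0/0.5/1/1 or 0/0.5/1/0.5.

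- The 3-df group-by-time test has about 41 to 79% power.
- The group main effect over all four visits has about 22 to 39%. If the full effect is already present at session 5 (0/1/1/1), it has about 63 / 52 / 44% at r = 0.3 / 0.5 / 0.7. At 0.3 that exceeds the adjusted session-10 figure, because it pools three post-baseline visits.
- A chance baseline gap above 0.5 SD has probability 2 × (1 − Φ(0.5/0.447)) = 0.26. At r = 0.6 such a gap moves an unadjusted session-10 difference by at least 0.6 × 0.5 = 0.3 SD. This matters only if the session-10 score is compared without baseline.

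**The case against.** The strongest reply is that C4 is silent on baseline, which is not the same as choosing badly. Its list of methods is introduced as inclusive, and a linear or mixed model with a session-1 covariate falls within it. The named families can also use baseline already. The hypotheses are worded as a decrease under active and not under sham, which is a group-by-time contrast, and the post-hoc step allows that contrast on 1 df between sessions 1 and 10. Against it the gain is only about 9 / 7 / 4 points at r = 0.5 / 0.6 / 0.7. If the error is pooled over the four visits (54 df, equal correlation), the contrast has about 59 / 69 / 81% power and the gap falls to about 6 / 3 / 1 points. That last comparison somewhat favours the contrast, because a multi-visit adjusted model would gain df too. A mixed model with arm means constrained equal at session 1 would, by theory, recover nearly all of the gain.

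The study is also declared exploratory, chance imbalance under randomisation is not bias, and every input beyond the sample size is assumed.

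All of this stands, and it limits the claim. A reader might infer that the planned analysis discards baseline and therefore loses power. The documents do not support that, because no model is specified. A reader might also take the lowest figures (22 to 39% for the main effect, or the low end of the 3-df test) as the power of this plan. Those apply only if those analyses are the ones used, and C4 does not say so.

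The reply does not remove the gap. The exploratory label explains the missing power calculation, but it does not tell the analyst which of several permitted analyses to run on 20 people.

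**Conclusion.** The point holds as an unspecified use of baseline with a cheap and usually more precise remedy. It does not hold as a demonstrated loss of power.

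Under the assumed 1-SD effect, the gain from adjustment depends on the comparator and the correlation. Against the session-10 score alone it runs from −3 points (r = 0) to 25 points (r = 0.7) and higher at 0.8. Against a change contrast it is 14 points at 0.3 and 1 point at 0.8. Against an equal-baseline constrained mixed model it is about nil. For moderate correlations (0.5 to 0.7) adjustment is better than both single-visit alternatives.

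It does not overcome the small sample: 80% power at those correlations still needs a difference of about 1.0 to 1.2 SD. The change is worth making because it costs almost nothing and fixes the choice in advance.

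**What to change.** Add one sentence to C4. For each outcome scale, fit sessions 5, 10 and six weeks as the outcomes, with arm, visit, arm-by-visit and the scale's own pre-stimulation session-1 score as a covariate, not as a repeated level. An equivalent alternative is a mixed model that keeps session 1 among the outcomes and constrains the arm means to be equal there. Name one of the two. Read Aim 1 from the adjusted active-sham difference at session 10 and Aim 2 from that at six weeks, each with a 95% interval.

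The cost is one sentence and one residual df (18 to 17 in the single-visit comparison). No new data or visits are needed. If a scale's session-1 score turns out nearly unrelated to its later scores, the price is about 3 points of power against the session-10 score alone.

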#### D. Material Inducements

Date most recently revised (m/d/y): 03/03/2015

Protocol Version (if applicable): 5.0

Compensation for time and effort will be offered for the measures administered in this study. Participants will receive \$60 as compensation for participation if they complete all 10 sessions of tDCS treatment. If the participants withdraw from the study before finishing, they will receive \$6 per session for each session in which they participated regardless if they were able to complete the full session.

### **E. Training of Research Personnel**

Prior to initiation of the study all research personnel will be trained in the specifics of this research project according to their role. Research personnel responsible for administering assessments and questionnaires will be trained by the PIs and Co-PIs. Ongoing training will occur as needed, especially if the study is amended and for review of the logistics and progress of this project.

All research staff will have completed research ethics training; including data management and procedures for maintaining data confidentiality and safety before being allowed to work on the project. Urine pregnancy tests will be done at Butler Hospital by a trained member of the research staff under the supervision of a licensed physician.

## **3) Human Subjects**

### **A. Subject Population** *(include number; gender; age; diagnosis; inpatient vs. outpatient; physical health; inclusion/exclusion criteria; rationale for use of special groups)*

To be eligible for participation in this study participants must be eighteen years or older with a diagnosis of CLBP chronic low back pain and meet the inclusion and exclusion criteria (see below). There are no exclusions based on race, ethnicity or gender. The plan is to consent up to thirty (30) volunteers with a goal of enrolling twenty (20) participants, ten (10) in the treatment group and ten (10) in the control group.

#### **Inclusion Criteria:**

1. At least eighteen (18) years old;
2. Chronic Low Back Pain - must be present for  $\geq 6$  months duration in the lumbar region, present more than half the days of the month, and on average be at a moderate level of severity in the last month ( $\geq 4$  on the DVPRS scale of pain intensity from 0 (no pain) to 10 (worst pain imaginable).
3. At least one trial of physician recommended medication (i.e. acetaminophen, NSAIDS, skeletal muscle relaxants)
4. Pre-existing opioid and non-opioid pain medication must be non-existent or stable (medications have not changed for one month)
5. Be able to understand, read and write English.
6. If female and of childbearing age, agree to use acceptable birth control during the study

Date most recently revised (m/d/y): 03/03/2015

Protocol Version (if applicable): 5.0

treatment period (oral contraceptives, history of tubal ligation, history of a hysterectomy, or a reliable barrier method) during the study treatment period.

**Exclusion Criteria:**

1. Lifetime DSM-IV diagnosis of bipolar disorder, schizophrenia, or other chronic psychotic condition;
2. Current DSM-IV diagnosis of substance dependence for alcohol, sedative/ hypnotic drugs, stimulants, or cocaine;
3. Current cancer, infection, or inflammatory arthritis
4. Broken skin or other lesions in the area of the electrodes
5. Uncontrolled medical problems, such as diabetes mellitus, hypertension, pulmonary or airway disease, heart failure, coronary artery disease, or any other condition that poses a risk for the subject during participation.
6. Presence of metal in the cranial cavity
7. Holes in the skull made by trauma or surgery
8. Pacemakers, medication pumps, and other implanted electronic hardware;
9. Pregnancy

**B. Recruitment and Consent Procedures**

Recruitment will primarily take place through referral from Butler Hospital clinicians or community providers. Advertisements will also be posted at Butler Hospital and online. See appendix for a text of these advertisements. Written informed consent will be obtained prior to clinical screening or administration of any measures or procedures. The consent process will be administered in person by a member the study team who has received research ethics training. The study team member will assess whether the potential participant understands the study procedures, and will ensure that all questions related to the study are answered. Participants will be informed that they may discontinue their participation at anytime without penalty.

After signing the consent form, potential participants will undergo further screening and collection of information with a trained research interviewer, designated by the principal investigators. The interviewer will collect demographic information (ex. age, gender, height, weight, racial/ethnic group, years of education, contact information) and further screen for study inclusion and contraindications of tDCS. The screening assessments are further detailed under specific study procedures.

Screening is expected to take up to one and a half hours (1 ½). The principal investigator/s will make the ultimate determination of whether the participant meets all the enrollment criteria and is appropriate to enter the study. Participants that do not meet the study criteria will be informed that based on the information collected, it has been determined they are not appropriate for the current study.

**C. Potential Risks**

There are minimal risks to be incurred from participating in this study. Specific risks related to the clinical and cognitive assessments (study questionnaires) and tDCS are described below.

Date most recently revised (m/d/y): 03/03/2015

Protocol Version (if applicable): 5.0

Participants may be uncomfortable sitting or lying for an extended period of time on the chair, recliner or stretcher due to their CLBP.

**Risks and discomforts due to Clinical and Cognitive Assessment Administration:** There are several questionnaires that the participant will be asked to answer. The time it takes to answer these questions may create frustration or fatigue. Answering the clinical symptom rating questions may involve sensitive information that could cause emotional reaction, embarrassment or discomfort. Previously undisclosed or unknown mental health problems may be identified.

**Risks due to tDCS:** There is some inherent risk with tDCS. Mainly there is a risk of skin irritation where the electrodes are attached to the scalp, which in the literature has been mostly limited to transitory redness. No toxic effects have been found, and the procedure carries few risks (Brunoni, et al., 2012). At the levels we are proposing, only a few publications report minor injuries, and the stimulation is widely considered to be “safe” (Bikson, et al., 2009). In rare cases, when skin around stimulation sites was non-intact, or when the stimulation was delivered for a long time without proper conductive solutions being applied to the electrodes, a few minor burns and skin lesions have been observed (Frank, et al., 2010). If electrodes/sponges are placed over preexisting skin lesions, such as vascular moles and angiomas there may be a greater conductance than the surrounding skin, increasing the risk of irritation or possible burns. Care is thus taken to exclude potential participants who exhibit broken or marked skin near the sites of the electrodes and to avoid abrading the skin prior to placing the electrodes (Loo et al. 2011). The electrodes in this study are soaked in normal saline. A study using the same amperage proposed in this protocol found no mood or cognitive changes due to tDCS (Iyer, et al., 2005). Transient, very rare post-tDCS effects have been found to include mild headaches, nausea, and insomnia (Poreisz, et al., 2007). In a prior study conducted by Drs. [name] and [name], eight of 40 participants reported sensations of itching, tingling, or burning under the tDCS electrodes; one participant reported mild dizziness. These sensations were consistent with those commonly reported for tDCS (Brunoni, et al., 2012). Less well-studied is the possibility of negative effects of tDCS on cognition and mood. A study using the same current amplitude as proposed in this protocol found no mood or cognitive changes due to tDCS, but this was with a single stimulation session (Iyer, et al., 2005). Several studies have used multiple sessions of tDCS of different brain regions successfully to reduce pain intensity from acute pain, neuropathic pain, and chronic pain from fibromyalgia (Antal, et al., 2008; Lefaucher, et al., 2008; Fregni et al. 2006) without significant adverse effects. Another potential concern is the risk of an undesired synergistic effect between a participant’s existing medication and tDCS. There are some reports in the literature of isolated instances of hypomanic or manic symptoms, typically noted with a longer treatment course than proposed in the current study or in patients with pre-existing bipolar diagnoses (Brunoni, et al., 2013; Galvez, et al., 2011) diagnosed bipolar disorder is an exclusion criterion for the present study. Nonetheless, comprehensive clinical studies quantifying the risk more precisely are clearly lacking. For the present study, participants will be closely monitored throughout the study to assess for any such effects. Participants will also be specifically instructed to tell the research staff if they notice an unwanted change in mood.

**D. Protection of the Subject** *(include: D.1. measures to minimize potential risks; D.2 measures to ensure confidentiality; D.3. data safety monitoring plan)*

Date most recently revised (m/d/y): 03/03/2015

Protocol Version (if applicable): 5.0

Participants will be reminded that they may stop participating in the study at any time for any reason with no adverse consequences to health or future relationships with Butler Hospital or Brown University. Participants will be encouraged to take breaks when needed. They will be reminded that they may refuse to answer any questions on the study questionnaires and they may stop the tDCS treatment session at any time.

